5.3 Exploratory Endpoints

The exploratory endpoint covered in this analysis plan is failure-free survival.

Failure free survival (FFS) is defined as no death, no relapse of underlying malignancy, and no new systemic immunosuppressive therapy for cGVHD. FFS will be right censored based on [Table 2](#):

Table 2: Date of Event or Censoring for Failure Free Survival

Situation	Date of FFS event or Censoring	Outcome
Death.	Date of death	Event
New subsequent cGVHD treatment	Date of starting the new subsequent cGVHD treatment	Event
Recurrent of malignancy	Start date of recurrent of malignancy	Event
Not known to have event at the data analysis cutoff date (this includes subjects who were known to have event after the data analysis cutoff date)	Date of last known date showing no evidence of event.	Censored

The distribution (median and Kaplan-Meier curve) will be provided using Kaplan-Meier estimates to evaluate FFS.

6. Safety

DLT review to determine RP2D will be performed in the Dose Level Review Meeting by the Sponsor in conjunction with the investigators after careful consideration of all available safety and laboratory information. This analysis plan will not cover this procedure.

Safety data collected in both Phase 1b and Phase 2 will be summarized together. Unless specified otherwise, all safety analyses will be based on All Treated Population.

6.1 Adverse Events

The verbatim terms used in the CRF by investigators to identify adverse events (AEs) will be coded using the Medical Dictionary for Regulatory Activities (MedDRA). Adverse events will be graded by the investigator according the National Cancer Institute common terminology criteria for adverse events (CTCAE) Version 4.03.

Drug-related adverse events are those assessed by investigator as being possibly related or related to study drug.

Treatment-emergent AEs are defined as those events that 1) occur on or after the first day of study drug, and within 30 days following the last dose of study drug or initiation of subsequent cGVHD therapy; 2) any event with missing onset date and its resolution date is during the treatment phase unless the event was indicated in the CRF that was present

before the first day of study drug; 3) any event that is considered study drug-related regardless of the start date of the event; or 4) any event that is present at baseline but worsens in severity or is subsequently considered drug-related by the investigator.

For each adverse event, the percentage of subjects who experience at least 1 occurrence of the given event will be summarized. In the event a patient experiences repeat episodes of the same AE, then the event with the highest severity grade will be used for purposes of incidence tabulations.

Summaries of AEs include:

- Incidence of AEs and serious adverse events (SAEs) by System Organ Class (SOC) and preferred term
- Incidence of AEs and SAEs by preferred term
- Incidence of drug-related AEs and SAEs

AE leading to study treatment discontinuation for the subjects who discontinued study drug due to AE, AE leading to dose reduction, and AEs leading to death will be summarized.

6.1.1 Adverse Events of Special Interest – Major Bleeding

Hemorrhagic events will be identified by hemorrhage Standardized MedDRA Query [SMQ] excluding laboratory terms and be tabulated. Major hemorrhage is a subset of hemorrhagic events which are grade ≥ 3 or serious or belong to central nervous system (CNS) hemorrhage/hematoma.

6.1.2 Other Safety Observations

Other Malignancies

Other malignancies are defined as new malignant tumors including solid tumors, skin malignancies and hematologic malignancies and are to be reported. They will be summarized based on following categories: melanoma skin cancer, non-melanoma skin cancer and non-skin cancer. Relapse of the underlying malignancy that was the basis for transplantation will not be included in this analysis.

Hypersensitivity Reactions

Hypersensitivity Reactions include angioedema, anaphylactic reaction, anaphylactoid reaction, anaphylactic shock, anaphylactoid shock, urticaria, drug hypersensitivity, and hypersensitivity. All treatment emergent hypersensitivity reaction events will be evaluated based on preferred terms.

Hypertension

Hypertension includes hypertension, essential hypertension, hypertensive crisis, blood pressure increase, systolic hypertension, and retinopathy hypertensive. All treatment emergent hypertension events will be summarized by preferred terms.

Interstitial Lung Disease

Interstitial Lung Disease (**ILD**) will be determined based on ILD SMQ excluding radiation alveolitis, radiation fibrosis - lung, and radiation pneumonitis, pulmonary radiation injury and transfusion-related acute lung injury. All treatment emergent ILD events will be summarized by preferred terms.

Severe Cutaneous Adverse Reaction

Severe Cutaneous Adverse Reaction (SCAR) will be determined based on following prefer terms:

Skin and subcutaneous tissue disorders SOC	Acute generalised exanthematous pustulosis
	Cutaneous vasculitis
	Dermatitis bullous
	Dermatitis exfoliative
	Dermatitis exfoliative generalised
	Drug reaction with eosinophilia and systemic symptoms
	Epidermal necrosis
	Erythema multiforme
	Exfoliative rash
	Oculomucocutaneous syndrome
	Skin necrosis
	Stevens-Johnson syndrome
	Toxic epidermal necrolysis
	Toxic skin eruption

All treatment emergent SCAR events will be summarized by preferred terms.

6.2 Clinical Laboratory Tests

All laboratory values will be converted to SI units and classified as normal, low, or high based on normal ranges of University of California, San Francisco.

The gradable laboratory parameters will be graded using the NCI CTCAE v4.03. The worst postbaseline toxicity grade will be summarized for hematologic and chemistry parameters.

Shift table will also be used to evaluate creatinine clearance.

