7.1.11. Laboratory

7.1.11.1. Hematology

Hematology parameters performed at local laboratory will include a complete blood count: white blood cells, red blood cells, hemoglobin, hematocrit, platelets, neutrophils, lymphocytes, monocytes, eosinophils, basophils and bands (if reported).

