7.1.11.2. Chemistry (Serum)

Serum chemistry parameters performed at local laboratory will include sodium, potassium, chloride, blood urea nitrogen (BUN), creatinine, glucose, calcium, total protein, albumin, AST, ALT, alkaline phosphatase, total bilirubin, lactate dehydrogenase (LDH), phosphate, uric acid, magnesium and bicarbonate.

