8.2. Treatment Phase

Following completion of the Screening Visit and once eligibility has been confirmed, subjects are enrolled. Enrollment should occur as close to the time of the expected first dose as possible, ie, not more than 3 business days prior to expected first dose with study drug.

During the treatment/follow-up period, DLT assessment will occur over a 28-day period. DLTs are defined in [Section 5.2.2](#). Local labs will be used to guide all dosing-related decisions.

Week 1 Day 1

Pre-dose

- Complete physical exam including weight.
- Vital signs and performance status (KPS)
- cGVHD assessment per NIH ([Appendix F](#) and [Appendix G](#)). This assessment must be a minimum of 14 days after the prior response assessment unless the subject's cGVHD is worsening. If the subject's cGVHD is clinically improved from the prior response assessment, then the first dose must be delayed and subject will need to be re-assessed at least 14 days later to confirm stable or worsening cGVHD. Please contact the Medical Monitor for any questions related to eligibility.
- Lee cGVHD Symptom Scale ([Appendix E](#))
- Photographic imaging of cGVHD
- Hematology
- Serum chemistry
- Urine pregnancy test for women of childbearing potential
- Review of baseline adverse events and concomitant medications (including corticosteroid requirements)
- Review of inclusion and exclusion criteria to confirm subject eligibility prior to first dosing
- Pharmacokinetic sampling (pre-dose)

- Pharmacodynamic sampling for PCYC (pre-dose)
- T/B/NK sampling for PCYC (pre-dose)
- Biomarkers sampling
- Immunosuppressant level – if applicable

Post Dose

- Administer ibrutinib at specified dose level, and then dispense remaining amount to subject for at-home dosing
- Provide drug diary and dosing instructions to subject
- Pharmacokinetic sampling for PCYC at 1, 2, 4, and 6 hours post-dose
- Pharmacodynamic sampling for PCYC (4 hours after first dose administration)
- T/B/NK sampling for PCYC (4 hours after first dose administration)
- Review adverse events

Week 1 Day 2**Predose**

- ^aPharmacokinetic sampling for PCYC (pre-dose before Day 2 drug administration)
 - ^aPharmacodynamic sampling for PCYC (pre-dose before Day 2 drug administration)
 - ^aT/B/NK sampling (pre-dose)
- ^a Within 24 hours of the first ibrutinib dose.

Week 2**Predose**

- Symptom-directed physical examination
- Hematology
- Serum chemistry
- Vital signs
- Immunosuppressant level – if applicable

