10.5. Safety Analysis

The safety variables to be analyzed include adverse events, clinical laboratory test results (hematology and chemistry), and other safety measurements. They will be summarized by descriptive statistics. No formal statistical testing is planned.

Exposure to ibrutinib first dose and reasons for discontinuation from study treatment will be tabulated.

Adverse Events

Adverse event parameters to be evaluated are the type, incidence, and intensity of adverse events; the relationship of adverse events to ibrutinib; and the action taken with respect to ibrutinib treatment due to adverse events.

The verbatim terms used in the eCRF will be coded using the Medical Dictionary for Regulatory Activities (MedDRA).

Treatment-emergent adverse events are those adverse events occurring after the first dose of study drugs and within 30 days following the last dose of study drug; any adverse event that is considered study drug-related regardless of the start date of the event; or any adverse event that is present at baseline but worsens after the first administration of study drug in severity or is subsequently considered drug-related by the Investigator. All treatment-emergent adverse events will be included in the analysis.

For each adverse event, the percentage of subjects who experience at least 1 occurrence of the given event will be summarized. The number and percent of subjects with treatment-emergent adverse events will be summarized according to intensity (NCI CTCAE v. 4.03) and drug relationship as well as categorized by system organ class and preferred term. Summaries, listings, datasets, or subject narratives may be provided, as appropriate, for those subjects who die, who discontinue treatment due to an adverse event, or who experience a severe or a serious adverse event.

Clinical Laboratory Tests

All laboratory values will be converted to standard international units and will be graded using the [NCI CTCAE v. 4.03](#).

A summary of the shifts in selected laboratory hematology and serum chemistry parameters from baseline to the worst toxicity grade during the study will be tabulated.

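### SAP 6.2 flags results from local laboratories against one university's normal ranges and names no upper limit of normal for CTCAE grading

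*SAP*

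**What the plan says.** **Where the results come from.** The Protocol synopsis describes multiple US centers. Protocol 7.1.11.1 has "Hematology parameters performed at local laboratory will include a complete blood count", and 7.1.11.2 places chemistry there too: "Serum chemistry parameters performed at local laboratory". The chemistry panel includes AST, ALT, alkaline phosphatase, total bilirubin and creatinine. Protocol 8.2 adds: "Local labs will be used to guide all dosing-related decisions".

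**How they are summarized.** Under SAP 6.2 every laboratory value is converted to SI units and then "classified as normal, low, or high based on normal ranges of University of California, San Francisco". The next paragraph reads "The gradable laboratory parameters will be graded using the NCI CTCAE v4.03", followed by "The worst postbaseline toxicity grade will be summarized for hematologic and chemistry parameters". Protocol 10.5 is similar, "All laboratory values will be converted to standard international units and will be graded using the" CTCAE v4.03, and adds shifts from baseline to the worst grade for selected parameters. Neither section says whose limits of normal feed a grade that depends on them.

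**How limits of normal are used elsewhere.** The renal and hepatic entry limits in Protocol 4.1 are multiples of ULN. Form A (Appendix F) has a ULN field beside the liver tests, and Appendix H scores liver response and progression in ULN multiples.

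**The concern.** Limits of normal belong to an assay and a laboratory. Converting to SI units aligns the units; it does not move a result from one laboratory's reference interval to another's. Applying one institution's interval to results produced elsewhere can call a locally normal value high, or a locally high value normal.

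Two outputs are exposed. The first is the normal/low/high classification itself, for which the SAP prescribes the university range outright. The second is any CTCAE grade defined through a limit of normal. For that the SAP supplies no other range, so a programmer would probably reach for the one it names.

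There is also an inconsistency within the trial. The same ALT result can be read against the ULN entered on Form A for liver response and against another institution's ULN in the safety summary. Because the liver is both a cGVHD domain and a site of possible toxicity, that makes the two sets of tables harder to reconcile. Safety and tolerability is the Phase 1b primary objective and a Phase 2 secondary one, so the laboratory tables will be read closely.

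**Working it through.** The plan gives no figure to reproduce on this point. The check has two parts: the text, and an illustration on stated assumptions.

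**1. What the text fixes and what it leaves open**

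| Item | Source | Limit of normal used |
|---|---|---|
| Normal/low/high class | SAP 6.2 | The university's, for all values |
| CTCAE laboratory grade | SAP 6.2, Protocol 10.5 | Not stated |
| Liver response | Protocol Appendices F and H | ULN entered on Form A |
| Neutrophil and platelet cut-offs | Protocol 5.3.1.4 | None; absolute counts |
| Creatinine clearance | SAP 3.1.9 | None; Cockcroft-Gault |

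The problem with the flags follows directly from the stated rule. The problem with the grades depends on how the gap in the second row is filled.

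**2. How far a reading can shift**

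The documents give neither the university's nor any site's ULN. Assume, for illustration only, that r = (university ULN) / (local ULN) lies between 0.7 and 1.4. Then

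multiple of university ULN = (multiple of local ULN) / r.

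| r | Result at 1.0 x local ULN reads as | Result at 3.0 x local ULN reads as | A 3 x university ULN cut-off equals |
|---|---|---|---|
| 0.7 | 1.43 x | 4.29 x | 2.1 x local ULN |
| 0.9 | 1.11 x | 3.33 x | 2.7 x local ULN |
| 1.0 | 1.00 x | 3.00 x | 3.0 x local ULN |
| 1.1 | 0.91 x | 2.73 x | 3.3 x local ULN |
| 1.4 | 0.71 x | 2.14 x | 4.2 x local ULN |

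At r = 0.7, results between 0.7 and 1.0 times the local ULN are flagged high although they are locally normal. At r = 1.4, results between 1.0 and 1.4 times the local ULN pass as normal although they are locally high.

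**3. The same point with one value**

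Take an ALT of 150 U/L and two laboratories with assumed ULNs of 35 and 60 U/L. Locally it is 150/35 = 4.29 x ULN at the first and 150/60 = 2.50 x ULN at the second, on opposite sides of 3 x ULN. A single reference ULN, U, gives one multiple for both. Since 150/3 = 50, any U below 50 puts both results above 3 x ULN, which is wrong for the second laboratory. Any U of 50 or more puts neither above it, which is wrong for the first. No choice of U is right for both.

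**4. Weight of one subject**

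With about 40 subjects at the recommended Phase 2 dose, one misclassified subject moves a percentage by 1/40 = 2.5 points.

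**The case against.** **The university range is tied only to the flags.** This stands. The grading sentence is separate and names no ULN source. A reader might infer that the SAP orders CTCAE grades to be computed from the university's ULN, and so that worst grades will be wrong. The text does not say that.

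**The grading consequence rests on definitions outside the documents.** This also stands. The CTCAE criteria are not reproduced, so which parameters are graded in ULN multiples, and where the boundaries lie, cannot be checked here. The 3 x ULN boundary used above appears in the documents as an entry limit and as a response threshold, not as a CTCAE grade.

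**The 150 U/L example contrasts two local ranges, which is what local grading would produce.** This does not defeat it. A single range yields one multiple, which must then disagree with one of the two laboratories.

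**One range gives uniform cut-offs and was prespecified.** It does give uniform cut-offs, and nothing in the protocol requires local ranges for these summaries. But uniform limits applied to results from different laboratories, with no normalization, are uniform in appearance only.

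**The reach is narrow.** This stands. Adverse events are graded by the investigator (SAP 6.1), and abnormalities judged clinically significant are recorded as adverse events (Protocol 7.1.6). Dosing follows local laboratories, and the safety analysis is descriptive, without formal testing (Protocol 10.5).

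**Conclusion.** The flagging rule in SAP 6.2 is unsound for local results. Normal/low/high classes can be wrong in either direction at any site whose ranges differ from the university's. For CTCAE grades the plan leaves the limit of normal unnamed, so misassignment of any grade that depends on one is a risk and not a demonstrated error.

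The size for this trial cannot be computed. The figures above rest on an assumed ULN ratio of 0.7 to 1.4, or on assumed ALT limits of 35 and 60 U/L, and show direction and plausible scale only.

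Two further inferences should be resisted. One is that every site but the university's own is misclassified: the documents neither list the sites nor say that the university is one, and a site with matching limits loses nothing. The other is that the trial's safety or efficacy conclusions are in doubt. The effect is confined to descriptive laboratory summaries. The primary endpoint, dosing decisions, investigator-graded adverse events and grades set by absolute counts are unaffected. This is a minor point, worth correcting because the correction is cheap.

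**What to change.** Amend SAP 6.2 to say that each value is classified as normal, low or high against the reference range of the laboratory that produced it, and that any CTCAE v4.03 grade defined by an upper or lower limit of normal uses that same range. Keep the university range only for results whose local range is missing, and flag those results in the listings.

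The cost is SAP wording plus a small data-management effort to collect and load local ranges. Protocol 12.6 already lists normal laboratory values among the essential documents that sites retain, although the documents do not say that these are in the data capture system. The price in presentation is less uniform cut-offs when results are pooled for display. Sample size, power and type I error do not change.

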 - a) Absolute neutrophil count (ANC) $\geq 1.0 \times 10^9$ /L and off growth factor support x 7 days
 - b) Platelets $\geq 30 \times 10^9$ /L and no transfusion support x 7 days
 - c) Hemoglobin ≥ 8 g/dL and no transfusion or growth support x 7 days
12. PT/INR < 1.5 x ULN and PTT (aPTT) < 1.5 x ULN (unless abnormalities are unrelated to coagulopathy or bleeding disorder).
13. ≤ 6 stools per day

14. Oxygen saturation after exertion maintained at $\geq 88\%$ on room air. If not, forced expiratory volume in 1 second (FEV1) $\geq 50\%$ on pulmonary function tests performed within 6 months of study entry.
15. Ability to understand and willingness to sign a written informed consent form (ICF).
16. Myeloablative or non-myeloablative allogeneic hematopoietic cell transplant for underlying hematological disease.
17. Female subjects who are of non-reproductive potential (ie, post-menopausal by history - no menses for ≥ 1 year; OR history of hysterectomy; OR history of bilateral tubal ligation; OR history of bilateral oophorectomy). Female subjects of reproductive potential must have a negative serum pregnancy test upon study entry.
18. Male and female subjects of reproductive potential who agree to use highly effective methods of birth control (eg, condoms, implants, injectables, combined oral contraceptives, some intrauterine devices [IUDs], complete abstinence¹, or sterilized partner) during the period of therapy and for 90 days after the last dose of ibrutinib.

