5.2.2. Definition of Dose Limiting Toxicities

The following DLT criteria apply only to Phase 1b of the study. After completing the DLT period (28 days), Phase 1b subjects will be evaluated by standard safety reporting.

A DLT is defined as any drug-related hematologic or non-hematologic toxicity Grade 3 or higher, with the following exceptions:

- Grade 4 nausea, vomiting, or diarrhea or Grade 3 diarrhea defined by ≥ 7 stools/day persisting for greater than 3 days despite best supportive care
- Grade 4 neutropenia or Grade 3 neutropenia persisting for greater than 14 days or Grade 3 neutropenia of any duration with fever
- For subjects with Grade 2 rash at entry, DLT will be progression to Grade 3 AND a doubling of % BSA involvement
- For subjects with Grade 3 rash at entry, DLT will be progression to Grade 4 OR a doubling of % BSA involvement

5.2.3. Phase 2

Following the establishment of the RP2D, the Phase 2 portion of the study will begin accruing additional subjects. Approximately 40 subjects (cumulative from both Phase 1b and Phase 2) will be treated with the RP2D. Subjects enrolled in the Phase 2 part of the study will have met the same inclusion/exclusion criteria as Phase 1b subjects and will be treated with the RP2D. Subjects continuing from Phase 1b and subjects enrolled in Phase 2 will continue to be treated unless they have intervening unacceptable toxicity or meet other criteria for subject discontinuation (see [Section 9](#)).

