5.3.1.4. Dose Modification for Adverse Reactions

During Phase 1b, ibrutinib will be stopped according to DLT rules in [Section 5.2.1](#) during the 28 day DLT window. Thereafter, subjects enrolled in Phase 1b will have ibrutinib modified or discontinued according to the guidelines in [Table 1](#).

For Phase 2, the dose of ibrutinib should be modified according to the dose modification guidelines in [Table 1](#) if any of the following toxicities occur:

- Grade 3 ANC (<1,000/ μ L) with an associated temperature $\geq 38.5^{\circ}\text{C}$
- Grade 4 ANC (<500/ μ L) for more than 7 days. Refer to [Section 6.1.1](#) for instruction regarding the use of growth factor support
- Grade 3 thrombocytopenia (<50,000/ μ L) in the presence of Grade ≥ 2 bleeding events
- Grade 4 thrombocytopenia (<25,000/ μ L)

- Grade 3 or 4 nausea, vomiting, or diarrhea if persistent, despite optimal anti-emetic and/or anti-diarrheal therapy
- Any other Grade 4 or unmanageable Grade 3 toxicity attributed to ibrutinib

Table 1: Ibrutinib Dose Modifications

Hematologic Adverse Events	
Occurrence	Action to be Taken
First	Withhold ibrutinib until recovery to an ANC ≥ 750 or platelets $> 25,000$ with no evidence of Grade ≥ 2 bleeding; may restart at original dose level
Second	Withhold ibrutinib until recovery to an ANC ≥ 750 or platelets $> 25,000$ with no evidence of Grade ≥ 2 bleeding; may restart at 1 dose level lower
Third	Withhold ibrutinib until recovery to an ANC ≥ 750 or platelets $> 25,000$ with no evidence of Grade ≥ 2 bleeding; may restart at 1 dose level lower
Fourth	Discontinue ibrutinib ^a
Non-Hematologic Adverse Events	
First	Withhold ibrutinib until recovery to Grade ≤ 1 or baseline; may restart at original dose level
Second	Withhold ibrutinib until recovery to Grade ≤ 1 or baseline; may restart at 1 dose level lower
Third	Withhold ibrutinib until recovery to Grade ≤ 1 or baseline; may restart at 1 dose level lower
Fourth	Discontinue ibrutinib ^a

^a. If ibrutinib is discontinued for toxicity, subject will end the Treatment Phase of the study.

For Grade 3 or 4 atrial fibrillation or persistent atrial fibrillation of any grade, consider the risks and benefits of ibrutinib treatment. If clinically indicated, the use of anticoagulants or antiplatelet agents may be considered for the thromboprophylaxis of atrial fibrillation ([Section 6.2.4](#)).

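### SAP 6.2 omits the baseline-to-worst-grade shift tables that Protocol 10.5 commits to, so an unchanged Grade 3 platelet count at entry appears as a Grade 3 laboratory result on ibrutinib

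*SAP*

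**What the plan says.** **Entry.** Inclusion criterion 11b (Protocol 4.1) sets the platelet floor at 30 × 10⁹/L: "Platelets $\geq 30 \times 10^9$ /L and no transfusion support x 7 days".

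**Grade limits.** Protocol 5.3.1.4 gives the limits per µL in its dose-modification list: "Grade 3 thrombocytopenia (<50,000" and "Grade 4 thrombocytopenia (<25,000".

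**Protocol analysis.** Section 10.5 says that shifts in selected hematology and serum chemistry parameters "from baseline to the worst toxicity grade during the study will be tabulated". It does not list the selected parameters.

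**SAP analysis.** Section 6.2 grades laboratory values by CTCAE v4.03 and then states: "The worst postbaseline toxicity grade will be summarized for hematologic and chemistry parameters". It adds a shift table for creatinine clearance. SAP 3.1.3 counts any measurement after the first dose as postbaseline, with no requirement that it differ from baseline. SAP 4.4 lists baseline hemoglobin and platelets among the baseline characteristics, in a summary that is not crossed with later grades.

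**The concern.** A worst-postbaseline-grade table shows new toxicity only if subjects start below the grade being counted. Here the entry criterion lets some subjects start at Grade 3 for platelets. The table as specified cannot tell a subject who was Grade 3 before the first dose and stayed there from one who fell to Grade 3 on treatment.

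This matters because the study has one arm, so each subject's own baseline is the only reference for a laboratory change. Safety and tolerability are the primary objective of Phase 1b and a secondary objective of Phase 2. Protocol Appendix B lists thrombocytopenia among the features seen in cGVHD. Protocol 1.8.3 lists Grade 3 or 4 thrombocytopenia and bleeding, with and without thrombocytopenia, among the risks of ibrutinib. Background disease and a possible drug effect therefore fall in the same row of the table, and the analysis that would separate them is in the protocol but not in the SAP.

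**Working it through.** There is no stated figure in the plan to reproduce. The check compares limits and then counts.

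**Step 1: does the entry range overlap Grade 3?**
- Platelet entry floor: 30 × 10⁹/L (Protocol 4.1, criterion 11b).
- Grade 3 upper limit: 50,000/µL = 50 × 10⁹/L. Grade 4 limit: 25,000/µL = 25 × 10⁹/L (Protocol 5.3.1.4).
- The Grade 3 band is 25 to <50 × 10⁹/L, so entry values of 30 to <50 × 10⁹/L lie wholly inside it. A count of exactly 50 × 10⁹/L is not Grade 3.

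**Step 2: does the same hold for neutrophils?**
- Entry floor: "Absolute neutrophil count (ANC) $\geq 1.0 \times 10^9$ /L and off growth factor support x 7 days", which is 1,000/µL. Protocol 5.3.1.4 places Grade 3 below 1,000/µL.
- A subject who meets the criterion is therefore not at Grade 3.

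**Step 3: what does each table show?** Take n = 40, the approximate number treated at the RP2D (SAP 1.2). Let k subjects enter at 30 to <50 × 10⁹/L and stay unchanged, and let t of the others fall to Grade 3 on treatment.
- SAP 6.2 worst-grade row: (k + t)/n.
- Shift table: t new Grade 3 cases among the n − k subjects not already at Grade 3.
- Each unchanged entry case adds 1/40 = 2.5 percentage points to the SAP row and nothing to the new cases.

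The documents do not give k, so the values below are assumptions. With t = 0 and exact (Clopper-Pearson) 95% intervals:

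| k (assumed) | SAP 6.2 Grade 3 row | 95% CI | New Grade 3 in shift table |
|---|---|---|---|
| 1 | 1/40 = 2.5% | 0.1 to 13.2% | 0 |
| 2 | 2/40 = 5.0% | 0.6 to 16.9% | 0 |
| 4 | 4/40 = 10.0% | 2.8 to 23.7% | 0 |
| 8 | 8/40 = 20.0% | 9.1 to 35.6% | 0 |

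With k = 4 and t = 2, the SAP row shows (4 + 2)/40 = 15.0% (5.7 to 29.8%). The shift table shows 2/(40 − 4) = 2/36 = 5.6% newly at Grade 3.

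**The case against.** The strongest reply is that this is an omission and not a conflict. The SAP's introduction says that it describes analyses outlined in the protocol, and nothing in it withdraws the shift summary. The word *also* in its creatinine-clearance sentence could be read as adding to shift tables already intended. Protocol 10.5 promises only selected parameters and does not name platelets. The worst-grade summary is legitimate in itself, no formal safety test is planned, and no stated decision rests on this table.

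Much of that stands. It limits the weight of the point and means that the worst-grade summary should stay. It does not close the gap, because the SAP specifies no hematology or chemistry shift table anywhere.

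The documents do not support four stronger readings that a reader might infer.

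- **That all cytopenias, or liver tests, are affected at Grade 3.** The neutrophil floor excludes Grade 3 at entry. The documents give no grade limits to set against the entry limits for hemoglobin, transaminases, alkaline phosphatase or bilirubin.
- **That adverse event rates are inflated in the same way.** Under Protocol 11.1.1 a pre-existing condition is not an adverse event unless it worsens. Under SAP 6.1 a baseline event becomes treatment-emergent only if it worsens or is later considered drug-related.
- **That SAP 6.2 distorts dose finding.** SAP Section 6 leaves DLT review outside its scope. A DLT is "any drug-related hematologic or non-hematologic toxicity Grade 3 or higher", so an unchanged count would not obviously qualify; the scenario needs both a fall and an attribution to the drug. What remains is a narrow wording question: Protocol 5.2.2 has entry-grade wording for rash but does not address subjects whose platelets are already Grade 3 at entry.
- **That every entry-Grade 3 subject inflates the row without a drug effect.** That holds for unchanged counts. A further fall may be a drug effect.

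**Conclusion.** The point holds for the laboratory-grade table, with platelets as the demonstrated case. Followed as written, SAP 6.2 reports an unchanged Grade 3 platelet count at entry as a Grade 3 postbaseline result, and it leaves out the analysis in Protocol 10.5 that would show the difference.

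The size is 2.5 percentage points per such subject in a table of 40. The total cannot be stated, because the number entering at 30 to <50 × 10⁹/L is not in the documents. The conclusion also assumes that the platelet limits in Protocol 5.3.1.4 are those applied when the SAP grades laboratory values. If subjects treated at another Phase 1b dose are included in the table, the denominator is larger and each case weighs slightly less.

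The efficacy conclusions are not affected. The change should be made because the protocol already calls for the table and, with no control arm, nothing else in the SAP's laboratory section links a subject's later grade to the grade at entry.

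**What to change.** In SAP 6.2:

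1. Keep the summary of worst postbaseline grade.
2. Add tables of baseline grade by worst postbaseline grade for hematology, with platelets named, and for chemistry, so that the SAP delivers what Protocol 10.5 describes. Use the baseline definition in SAP 3.1.2.
3. Report the number and percent of subjects whose grade worsened from baseline.

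Hematology and chemistry are already scheduled at screening, before the first dose and throughout treatment (Protocol Appendix A). The cost is a few lines of SAP text and standard output, with no added burden on subjects or sites.

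Separately, the sponsor should reconcile Protocol 5.2.2 with inclusion criterion 11b for subjects whose platelets are already Grade 3 at entry. How that is resolved is a clinical decision for the sponsor.
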